Few studies have examined the incidence according to the currently used "European Organization for Research and Treatment of Cancer/Invasive Fungal Infections Cooperative Group and the National Institute of Allergy and Infectious Diseases Mycoses Study Group" (EORTC/MSG) guidelines for a proven, probable, or possible IMI (3). An Australian 10-year epidemiological study, however, indicates an incidence of invasive aspergillosis in patients treated for acute myelogenous leukemia (AML) and acute lymphoblastic leukemia (ALL) of (14/232) 6%, (33/1216) 2.7 %, respectively (4, 5). Only few epidemiologic reports have been performed in Denmark or Scandinavia (6).

Despite progress in the diagnosis, prevention, and management of IMI, the reported mortality rates are often high. In an epidemiologic multicenter study, the main proportion of molds was A. fumigatus, with a mortality rate of 30% (7). A number of risk factors have been associated with IMI, among these, corticosteroid exposure, neutropenia, as well as different chemotherapy and conditioning regimens. However, few studies have addressed this in children with cancer, and knowledge regarding individual risk prediction for developing IMI in immunosuppressed children remains sparse (8, 9). Besides established risk factors for IMI, other treatment-related toxicities, including metabolic changes and gastrointestinal toxicity, may also be related to infectious morbidity (10-12).

Our aim is to obtain an epidemiological overview of IMI in children receiving first-line treatment for ALL or AML in Denmark and identify possible risk factors, including treatment-related adverse effects.

Objectives

1. To determine and compare the incidence of IMI in childhood AML and ALL during first-line chemotherapy in Denmark.

2. To determine and compare the mortality of IMI in childhood AML and ALL during first-line chemotherapy in Denmark.

3. To explore risk factors for IMI in childhood AML and ALL during first-line chemotherapy in Denmark.

METHODS

Study design

A retrospective nationwide multicenter, open cohort study of all children who received first-line chemotherapy against acute leukemia from January 1st, 2008, to December 31st, 2022, in a Danish pediatric oncology unit; this includes data from the four Danish tertiary pediatric oncology units at Rigshospitalet, Aarhus University Hospital, Odense University Hospital, and Aalborg University Hospital.

Study population

Any patient (<18 years) who initiated first-line chemotherapy against primary ALL or AML at any of the four Danish departments of pediatric oncology from January 1st, 2008, to December 31st, 2022 (**Figure 1**). The eligible sample of children has been estimated to correspond to approximately 800 individuals who will be included in the cohort and subsequently be referred to as the intention-to-survey (ITS) population.

Data sources

Patients from the four Danish departments of pediatric oncology treating pediatric ALL and AML will be identified by searching the Danish Childhood Cancer Registry. The register holds data since 1985 on all children < 15 years with cancer and all children 15-17 years of age treated at a pediatric oncology department (13).

After cohort inclusion, data will be collected from the databases below, including the patient's medical records, hospital administrative databases, and national databases when applicable. The data for all cohort patients will be collected as listed in **Table 2**. For IMI patients only, additional data for a qualitative synthesis is collected, as detailed in **Table 3**.

- **The Danish Microbiology Database** is a nationwide database carrying all microbiology test results. We will search the database to identify factors that fulfill the criteria of direct or indirect proof of mold infection (Table 1).
- **The Danish Pathology Register is** a nationwide database carrying all pathology test results. We will search the database to identify histopathologic proof of mold infection.
- We will search the regional radiology databases for proof of mold infection, as this is not a nationwide database. We will explore the databases for radiologic interpretations of computed tomographies and magnetic resonance imaging to identify the IMI criteria (Table 1).
- Regional databases of blood test results will be searched to identify the neutrophilic count at the time of mold diagnosis in the IMI group and further to find proof of pancreatitis or hyperlipidemia.
- Patient records will be scrutinized to identify pre-leukemia comorbidities, leukemia diagnosis, and risk group, among other information, as listed in table 2 and table 3.

Data collection will start in April 2023.

Outcome variables

The primary outcome is defined as IMI. To identify patients who develop IMI, all cohort patients will have their pathology, microbiology, and radiology records reviewed for documentation, qualifying for EORTC/MSG criteria for either proven or probable disease. As recommended for epidemiological studies, the possible disease category has been left out (3). In brief, IMI is classified as proven when there is tissue damage and histopathologic, cytopathologic, or microscopic documentation of infection; a fungal DNA amplification by polymerase chain reaction (PCR) in paraffin-embedded tissue; or culture samples from a normally sterile site suspicious of infection.

The probable IMI requires the presence of a host factor (hematologic malignancy, among others), clinical features, and mycological evidence. Clinical features comprise specific clinical, bronchoscopic, and/or radiologic findings showing signs of tracheobronchitis, pulmonary, sino-nasal, or central nervous system (CNS) infection. The mycological documentation is either direct, usual cultures from a non-sterile site (i.e., mold found in sputum) or indirect detection of Aspergillus galactomannan antigen. The criteria for "possible disease" are identical to "probable disease" but without the presence of mycological evidence (3) (see table 1). The outcome variable is binary (i.e., IMI yes or no), but an additional analysis will be made for the IMI subgroups (i.e., IMI proven or probable).

Exposure variables

The putative risk factors, referred to as 'exposures', are obtained from the patient's medical charts and corresponding paraclinical databases. These include antifungal medication, its type, dosing, and duration. It will be registered whether this was given as primary prophylaxis, treatment, or as secondary prophylaxis (after treated IMI). Also, preleukemic morbidities, treatment protocol, neutrophil granulocyte count at leukemia diagnosis, concomitant infections, and blood transfusion history, as a means of generalized toxicity, will be registered. Furthermore, therapy-related adverse effects, including gastrointestinal toxicity, neutropenic colitis, and treatment-related metabolic changes, including hyperglycosemia, pancreatitis, and hyperlipidemia (Table 2).

Observational period

The period of IMI risk is defined as the period of active anticancer treatment. Exposure data from cohort subjects are collected from the date of cancer diagnosis until finished first-line chemotherapy, IMI occurrence, death, emigration, switching to a non-first-line treatment (e.g., treatment for induction failure or relapse), or 31st December 2022 (end of the study period), whichever comes first. For the IMI patients, we will also collect IMI outcome (cured, deceased, or emigrated) data after the IMI diagnosis for a narrative description of this group and to calculate the fatality rate.

Figure 1. STROBE flow diagram presenting the study design. ITS, intention to survey; ALL, acute lymphoblastic leukemia; AML, acute myelogenous leukemia (AML); IMI, invasive aspergillus.

Bias and limitations

As the cohort study is observational and retrospective, the study relies on data extracted from medical charts. To avoid imprecise documentation, the predominant amount of data is exact (i.e., blood values), whereas more loosely medical chart statements will be avoided as far as possible. There is no risk of 'recall bias,' as no patients or health care professionals will be contacted.

Another limitation in our study could be a small number of IMI patients and exposures; this would yield a low power and could be the reason for inconclusive findings. To avoid this and type 1 errors, we will report measures of association with confidence intervals; if these exclude measures of clinical interest, we will assume that our study is not limited by sample size and number of events (say, if the 95% confidence intervals around the Hazard Ratio reasonably precise [95%CI: 0.80 to 1.25]).

During the 15 years of study, the treatment protocols have changed. We will apply the analyses to the whole population and do subgroup analyses for patients according to their specific treatment protocols.

Statistical methods

The primary analyses will be based on the Intention to Survey (ITS) population, i.e., based on the Full Analysis Set (see Figure 1 illustrated above). To assess distributions and check for errors, variables will be summarized before analysis. The frequency of IMI in the cohort will be determined by calculating the cumulative incidence.

Hazard ratios (HR) for ALL relative to AML will be estimated, with two-sided 95% confidence intervals, based on a Cox proportional-hazards model, with AL-type as the primary covariate. Equivalence will be shown if the limits of the two-sided 95% confidence interval exclude (less than) 0.80 and (more than) 1.25. Crude incidence rates will be expressed in patients with IMI events per 100 patient-years, with two-sided 95% confidence intervals. No multiplicity adjustments will be applied. P values, without adjustment for multiplicity, will be produced for all listed objectives. To identify independent risk factors for the development of IMI, regression models will be applied to explore which children were more likely to develop IMI (e.g., AL-type, sex, age at diagnosis, and related toxicities, see table 2).

All *P* values and 95% confidence intervals will be two sided. We will not apply explicit adjustments for multiplicity, rather we will analyze the secondary objectives in a prioritized order: The analyses of these will be performed in sequence until one of the analyses fails to show the statistically significant difference, or until all analyses have been completed at a statistical significance level of 0.05. The key secondary statistical tests will be reported with *P* values for hypothesis tests and claims of statistical significance.

Analyses will be performed using STATA software version 17 (StataCorp. 2021. Stata Statistical Software: Release 17. College Station, TX: StataCorp LLC.).

Patient and public involvement statement

As all data will be retrieved from patients no longer in active treatment, patients are not actively involved and were unfortunately not included in designing this study.

Ethics and dissemination

The relevant Danish authorities have approved the study, including the regional research legislation office "Regionssekretariat og jura, Syddanmark" (journal no. 22/7692), "Region Syddanmarks Interne Fortegnelse" (journal no. 22/15850), and by the involved departments. Other ethics approval has not been required for this study.

The study will be registered at Clinical.Trials.gov. The study acts under the Declaration of Helsinki. No patient will be contacted and is not exposed to any inconvenience. All data are confidential and will

be processed in accordance with the General Data Protection Regulation (GDPR) and The Danish Data Protection Act.

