Abbreviations: BAL, bronchoalveolar lavage; CSF, cerebrospinal fluid; CT, computed tomography; PCR, polymerase chain reaction; IMI, invasive mold infection.

alf culture is available, append the identification at the genus or species level from the culture results.

^b Tissue and cells submitted for histopathologic or cytopathologic studies should be stained using Grocott-Gomori methenamine silver stain or periodic acid Schiff stain to facilitate inspection of fungal structures. Whenever possible, wet mounts of specimens from foci related to invasive fungal disease should be stained with a fluorescent dye (eg, calcofluor or blankophor).

Recovery of Aspergillus species from blood cultures rarely indicates endovascular disease and almost always represents contamination.

^dHematologic malignancy refers to active malignancy, in receipt of treatment for this malignancy, and those in remission in the recent past. These patients would comprise largely acute leukemias and lymphomas, as well as multiple myeloma, whereas patients with aplastic anemia represent a more heterogeneous group of individuals and are not included. The list of host factors has been shortened.

Table 2. Characteristics and putative risk factors to be collected from all cohort patients.

	VARIABLE
Age (number in years)	Numerical
Sex (male/female)	Binary
Treating facility (Copenhagen/Århus/Odense/Aalborg)	Categorical
Pre-leukemia comorbidities	Categorical
ALL diagnosis: treatment protocol, risk group and CNS-status	Categorical
AML diagnosis: treatment protocol, risk group, FAB, and CNS-status	Categorical
Date of malignancy diagnosis	-
Name of treatment protocol	Categorical
Criteria met for IMI (proven/probable)	Categorical
Localization of IMI	Categorical
Neutrophil granulocyte count at leukemia diagnosis	Numerical
Anemia and red blood cell transfusion requirement (quantity)	Numerical
Thrombocytopenia and platelet transfusion requirement (quantity)	Numerical
Primary antifungal prophylaxis (type/dose/duration)	Categorical
Fungal infection other than IMI (fungi in a sterile site) (localization and type)	Categorical
Concomitant infections (bacteria in a sterile site) (localization and type)	Categorical
Neutropenic colitis (only radiological evidence: MRI, CT, plain film of the abdomen, US: bowel wall thickening > 4 mm, mesenteric stranding,	Binary
bowel dilatation, mucosal enhancement, or pneumatosis) (yes/no)	
Pancreatitis (> x3 upper limit of amylase/lipase) (yes/no)	Binary

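### Corticosteroid exposure and on-treatment neutropenia are recorded only in children with IMI, so Objective 3 cannot estimate them individually or call its toxicity associations independent of them

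*Combined protocol and SAP*

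**What the plan says.** The background text before the objectives states: "A number of risk factors have been associated with IMI, among these, corticosteroid exposure, neutropenia". Objective 3 is to explore risk factors for IMI.

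Data sources assigns Table 2 to every cohort patient. Of Table 3 it says: "For IMI patients only, additional data for a qualitative synthesis is collected". Corticosteroid therapy and severe neutropenia (days before IMI, and the count on the day of IMI diagnosis) are both Table 3 items. The same section limits the on-treatment neutrophil search to the IMI group, while the same blood-test databases are also searched for pancreatitis and hyperlipidemia, which are Table 2 items.

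For the whole cohort, Table 2 lists "Neutrophil granulocyte count at leukemia diagnosis" and no corticosteroid item. Exposure variables agrees, naming "neutrophil granulocyte count at leukemia diagnosis, concomitant infections, and blood transfusion history, as a means of generalized toxicity". Toxicities in Table 2 carry no onset date; one entry, for example, is "Pancreatitis (> x3 upper limit of amylase/lipase) (yes/no)".

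Statistical methods says: "To identify independent risk factors for the development of IMI, regression models will be applied". It points to Table 2 for the candidate variables. Bias and limitations undertakes to "do subgroup analyses for patients according to their specific treatment protocols" and does not mention the missing case-versus-non-case data.

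**The concern.** A hazard ratio for a factor needs that factor in children who did not develop IMI as well as in those who did. Here two factors that the protocol itself cites are held for cases only. There are two consequences.

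- Objective 3 will give no individual-level estimate for corticosteroid exposure or on-treatment neutropenia.
- The toxicities that are held for everyone (neutropenic colitis, insulin-dependent diabetes, pancreatitis, hyperlipidemia) may travel with those factors. Neutropenic colitis is tied to neutropenia by name, and corticosteroid exposure could plausibly contribute to diabetes and hyperlipidemia. An association found for a toxicity could partly reflect the unmeasured factor and still be reported as independent.

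**Working it through.** The documents give no event, power or sample-size figure for Objective 3, so there is none to reproduce. The main check is on the text; the arithmetic only gives scale.

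**1. Who has which variable**

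| Item | All patients (Table 2) | IMI cases only (Table 3) |
|---|---|---|
| Neutrophils at leukemia diagnosis | yes | – |
| Neutropenia during treatment | no | yes |
| Corticosteroid therapy | no | yes |
| Treatment protocol, risk group | yes | – |
| Red-cell and platelet transfusion quantity | yes | – |
| Date of toxicity onset | no | no |

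No non-case has either factor during treatment, so no hazard ratio can be formed for it.

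**2. Expected cases.** Inputs: about 800 children (Study population); invasive aspergillosis in 14/232 AML and 33/1216 ALL patients (background text); AML share s assumed at 0.10 to 0.25.

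Cases = 800 × [s × 14/232 + (1 − s) × 33/1216]

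- s = 0.10: 4.8 AML + 19.5 ALL = 24.4
- s = 0.25: 12.1 AML + 16.3 ALL = 28.4

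That leaves about 772 to 776 non-cases. The rates are for aspergillosis, so all mold infections may be more. With two equal protocols per leukemia type (assumed), a protocol subgroup holds 2.4 to 6.0 AML or 8.1 to 9.8 ALL events.

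**3. Possible spurious association.** For an omitted binary factor with relative risk RR for IMI, present in a share p1 of children with the toxicity and p0 of those without, a toxicity with no effect shows

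[1 + (RR − 1)p1] / [1 + (RR − 1)p0]

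All inputs are assumed: RR 2 to 5, p1 0.4 to 0.7, p0 0.2 to 0.3.

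- Smallest: RR 2, 0.4 v 0.3: 1.4/1.3 = 1.08
- Largest: RR 5, 0.7 v 0.2: 3.8/1.8 = 2.11
- If proxies halve p1 − p0: 1.35/1.3 = 1.04 and 2.8/1.8 = 1.56

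**4. What the study could detect.** At 80% power and two-sided 5%, with d = 24 to 28 events and exposure prevalence p = 0.2 to 0.5:

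HR = exp(2.80 × √(V / (d × p(1 − p))))

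V is the variance inflation from adjustment. The adjusted rows assume a strong relation (each factor present in 70% with the toxicity v 20% without; two factors independent given toxicity).

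| Full cohort | V | Detectable HR |
|---|---|---|
| Unadjusted | 1 | 2.88 to 4.18 |
| Adjusted for one factor | 1.24 to 1.34 | 3.40 to 4.90 |
| Adjusted for both | 1.47 to 1.68 | 3.9 to 5.7 |

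These treat the toxicity as a fixed yes/no exposure, so they are approximate for time-dependent analysis.

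**The case against.** The strongest reply is that this is a scope choice. Objective 3 and the regression are worded as exploration, Table 3 is labelled qualitative, and the background introduces the toxicities as additional to established factors. Independent is also often used loosely to mean mutually adjusted. This stands in part: keeping Table 3 descriptive is a legitimate choice. But exploratory wording does not make an association independent of factors that were not measured, and the limitations section does not disclose the gap.

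Second, the plan is not without control. Protocol and risk group index planned therapy at group level, and the protocol subgroups use them. Transfusion quantities are recorded for each child as a marker of general toxicity and are a crude individual proxy for marrow suppression. This stands: a reader might infer that the toxicity associations are wholly unadjusted for these factors, and that is not so. None of these items, however, gives a child's own neutropenia, corticosteroids actually received, or their timing, and events per protocol will be few.

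Third, nearly every bias input is assumed, and the range starts at 1.04. This stands too. The figures show that distortion is possible, not that it occurs.

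Fourth, Bias and limitations says that "more loosely medical chart statements will be avoided as far as possible", which weighs against abstracting corticosteroid exposure from charts. It does not weigh against neutrophil counts, which are laboratory values.

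**Conclusion.** The gap is real and rests on the text alone: neither factor can be estimated for individuals, and the independence wording in Statistical methods is unsupported. It should be corrected.

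The conclusion stops there. A reader might go on to infer that the toxicity results will be materially biased, or that Objective 3 as a whole fails. The documents support neither. They give no strength or prevalence for the omitted factors by toxicity, so the bias is unknown (1.04 to 2.11 across the assumed inputs), and associations for the Table 2 variables can still be explored and reported as such. Objectives 1 and 2 do not depend on these variables. Nor do the documents show that the omission was an oversight.

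Collecting the data would not make this a precise analysis. With about 24 to 28 cases, which depends on the assumed AML share and the cited aspergillosis rates, only large hazard ratios are detectable.

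**What to change.** 1. **Neutropenia for everyone.** Extract dated neutrophil counts during therapy for all cohort patients from the regional blood-test databases already searched, and add them to Table 2. Analyse neutropenia as a time-dependent covariate, lagged before each risk time. Record the onset date of each toxicity and enter it as a time-dependent exposure from that date, one toxicity at a time, with and without the neutropenia adjustment. State that neutropenia after toxicity onset may be a consequence of the toxicity, so adjustment can remove part of its effect. With AL-type stratified, this is two parameters: 24.4/2 = 12.2 to 28.4/2 = 14.2 events each.

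2. **Wording.** In Statistical methods, describe the aim as finding factors associated with IMI. In Bias and limitations, state that individual corticosteroid exposure (and neutropenia, if step 1 is not done) is unmeasured in non-cases, and that protocol, risk group and transfusion quantities control it only in part.

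3. **Optional.** Abstract corticosteroid exposure for about four risk-set controls per case (4 × 24.4 = 97 to 4 × 28.4 = 113), matched on AL-type and time since leukemia diagnosis, with a common index date for cases and controls. Adjusting for both factors raises the detectable HR in the strong-relation scenario to about 3.9 to 5.7 in the full cohort, and higher with sampled controls.

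**Cost.** Step 2 is two wording changes. Step 1 is a larger extract from databases in use, toxicity dates, and a check that approvals cover these data in non-cases. Collection was due to start in April 2023, so an extract may have to be reopened. Step 3 adds chart work on about 100 controls, which is debatable for an exploratory objective, and matching reduces the corticosteroid contrast. No patient contact is needed.

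### Unadjusted 95% confidence intervals do not avoid type 1 errors, and no other error control covers the individual exposures within Objective 3

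*Combined protocol and SAP*

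**What the plan says.** Bias and limitations names the small number of IMI patients and exposures as a possible cause of low power and inconclusive results. It continues: "To avoid this and type 1 errors, we will report measures of association with confidence intervals". The same sentence then gives a precision rule: if the intervals exclude values of clinical interest, sample size will not be regarded as limiting. Its example is a hazard-ratio interval of 0.80 to 1.25.

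Statistical methods sets the inferential rules:
- P "values and 95% confidence intervals will be two sided".
- "No multiplicity adjustments will be applied", and "P values, without adjustment for multiplicity, will be produced for all listed objectives".
- For multiplicity, "we will analyze the secondary objectives in a prioritized order", stopping at the first non-significant result or when all analyses are "completed at a statistical significance level of 0.05".
- Key secondary tests are to be reported with P "values for hypothesis tests and claims of statistical significance".

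Objective 3 is worded as exploring risk factors. Statistical methods gives the aim of the regression models as identifying independent risk factors. It lists leukemia type, sex, age and toxicities as examples and points to Table 2, headed "Characteristics and putative risk factors to be collected from all cohort patients". The number of factors to be tested and the rule for building the models are not stated.

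**The concern.** The plan assigns a property to confidence intervals that they do not have. Low power and false-positive findings are different problems. An interval shows how imprecise an estimate is, but reporting it does not change how often a null factor appears to be associated.

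The practical risk lies in Objective 3. Many toxicities and characteristics will be related to a small number of IMI events. If the interval for one of them (pancreatitis or hyperlipidemia, say) excludes 1, it could be published as an independent risk factor, and the protocol could be cited as having guarded against chance. With few events, a false lead is hard to tell from a real one.

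**Working it through.** The plan gives no family-wise error rate, power or event target, so there is no figure of its own to reproduce beyond the per-test level: 1 − 0.95 = 0.05.

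**1. Interval and test.** The Wald interval is log HR ± 1.96 × SE. It excludes log HR = 0 exactly when |log HR / SE| > 1.96, which is two-sided P<0.05. Showing the interval beside or instead of the P value leaves the error per null factor at a nominal 5%.

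**2. Number of candidate factors, k (own count from Table 2).**
- Table 2 has 22 rows. Date of diagnosis, IMI criteria, IMI localization and cancer outcome cannot serve as exposures: 22 − 4 = 18.
- Adding leukemia type gives 19.
- Merging the separate protocol row and the diabetes-duration row into related rows gives 18 − 2 = 16 (without leukemia type).
- Replacing the ALL, AML and protocol rows by protocol, risk group, CNS status and FAB once each, then adding leukemia type, gives 18 − 3 + 4 + 1 = 20.

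**3. All factors null and independent.** The chance of at least one false factor is 1 − 0.95^k, and the expected number is 0.05k.

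| k | At least one | Expected number |
|---|---|---|
| 10 | 40.1% | 0.50 |
| 13 | 48.7% | 0.65 |
| 14 | 51.2% | 0.70 |
| 16 | 56.0% | 0.80 |
| 18 | 60.3% | 0.90 |
| 19 | 62.3% | 0.95 |
| 20 | 64.2% | 1.00 |

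If leukemia type has a true effect, one null drops out: k = 19 becomes 18 nulls, or 60.3%.

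**4. Correlated factors (assumed common correlation between test statistics, simulated).**

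| Correlation | k=16 | k=18 | k=19 |
|---|---|---|---|
| 0.1 | 54.8% | 58.9% | 60.9% |
| 0.2 | 51.7% | 55.5% | 57.2% |
| 0.3 | 47.7% | 51.0% | 52.5% |
| 0.4 | 42.7% | 45.6% | 47.0% |
| 0.5 | 37.5% | 39.8% | 40.9% |

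**5. Sparse events.** The introduction cites invasive aspergillosis in 14/232 AML and 33/1216 ALL patients in Australian data. With about 800 children and an assumed ALL share s, expected events are 800 × [s × 33/1216 + (1 − s) × 14/232]. This gives 29.7 at s = 0.7 and 24.4 at s = 0.9.

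As an approximation to the Cox test, the exact size of a Wald log-odds-ratio test was computed for 20, 26 and 32 events among 800, with exposure prevalence from 3% to 50%. It lay between 0.0145 and 0.0456, apart from one setting at 0.0664. Putting the real size into 1 − (1 − size)^k, with independent tests:
- Size 0.04: 48.0% (k=16), 52.0% (k=18), 54.0% (k=19).
- Size 0.035: 43.4%, 47.3%, 49.2%.
- Size 0.03: 38.6%, 42.2%, 43.9%.
- Size 0.02, near the low end: 27.6%, 30.5%, 31.9%.

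**6. Pressure the other way.** Multi-level categories, subgroups by treatment protocol and the separate proven/probable analysis all add tests. For example, k = 24 independent tests give 70.8%.

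**7. The 0.80 to 1.25 rule.** For an interval that narrow around HR = 1, SE = ln(1.25)/1.96 = 0.114, and the events needed are 1/[a(1 − a)SE²] for exposure share a. This is 309 at a = 0.5 and 606 at a = 0.15, against about 24 to 30 expected. The rule concerns precision, and at these event numbers it gives no practical protection against false positives.

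**The case against.** The strongest defence has four parts.

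- **The plan is candid and exploratory.** It says openly that nothing is adjusted, and Objective 3 is worded as exploration. Exploratory work need not adjust. This stands, and it is why adjustment is not required here. It does not rescue a statement that type 1 errors are avoided, and Statistical methods also speaks of identifying independent risk factors.
- **The paragraph is about power and precision, so type 1 may be a slip for type 2.** This is possible but cannot be shown. The sentence would still be wrong, because reporting an interval does not avoid a type 2 error; it shows the imprecision behind one.
- **There is a sequential rule.** A reader might infer that nothing in the plan limits false positives. That goes too far: if Objective 3 came after an objective that failed, the sequence would stop before it. Once Objective 3 is reached, however, the rule says nothing about the order or error level of its individual exposures.
- **The number of tests is open.** Table 2 mixes characteristics with putative risk factors and is not a list of tests. Red-cell and platelet transfusion needs, and the metabolic toxicities, are plausibly correlated. This stands.

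Because of the last part, a reader might infer from the equivalence of interval and test that at least one false risk factor is more likely than not. The documents do not support that. It would need at least 14 effectively independent, truly null tests, each at a real 5% level (k = 13 gives 48.7%). Moderate correlation or sparse-event conservatism can bring the figure below 50%, and added subgroup tests can raise it again.

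**Conclusion.** The point holds as a fault in what the plan claims. Unadjusted 95% intervals give no protection against type 1 error beyond that of the 0.05 test. The plan sets no error control across the exposures within Objective 3.

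The size depends on assumptions that the documents do not settle. With 16 to 20 null, independent factors, the chance of at least one false factor is about 56% to 64%. With common correlation up to 0.5, or with real test sizes of about 0.03 to 0.04, it is roughly 40% to 60%. Sizes near 0.02, or correlation and conservatism together, would lower it further. None of the figures calculated for the 16 to 20 factors is near 5%, and the conclusion does not depend on which side of 50% applies.

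The single pre-named comparison of ALL with AML is not affected by this count. What is affected is how firmly the study may speak about individual exposures.

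**What to change.** In Bias and limitations, delete the statement that confidence intervals avoid type 1 errors. Keep the intervals, described as a measure of precision.

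In Statistical methods, state for Objective 3 that:
- the risk-factor results are hypothesis-generating;
- the exposures are listed in advance and every one is reported, whatever its result;
- no claim of statistical significance, or of an identified independent risk factor, will rest on a single unadjusted interval or P value.

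A multiplicity-adjusted column, such as Benjamini-Hochberg q-values across the listed exposures, is optional. It is one reasonable choice for an exploratory analysis, and it can be defined only once the list and models are fixed.

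The cost is a few sentences of protocol text and a fixed exposure list, with no new data. The downside is that conclusions on individual exposures become less firm.
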